2.2 Analysis sets

The Full Analysis Set (FAS) and Safety Set both comprise all participants that received any investigational drug.

The enrolled population will consist of all participants who complete the screening period. For rules of exclusion criteria of analysis sets see Appendix 5.5.

2.2.1 Subgroup of interest

Weight brackets (≥ 8.5 -13 kg, > 13 -17 kg, > 17 -21 kg) are subgroups of interest. Weight brackets are defined by body weight measurements at Screening visit 2. Data will be summarized by weight bracket and overall.

2.3 Patient disposition, demographics and other baseline characteristics

2.3.1 Patient disposition

Disposition will be presented for all participants, which will include the following:

- The number of participants screened
- The number (%) of screened participants who screen failed and the reasons for screen failure (inclusion/exclusion criteria, withdrew consent, and/or other) will be summarized. A listing of reasons for screen failure will be provided for all participants who screen failed.
- The number (%) of participants in each weight bracket (≥ 8.5 -13 kg, > 13 -17 kg, > 17 -21 kg), and overall, for the FAS.
- The number (%) of participants who completed the study, defined as all participants with a final scheduled visit at Month 12 conducted either remotely or at the study site
- The number (%) of participants who discontinued from the study and the associated reasons

For participants who discontinued due to AE, a separate summary table will be produced in order to detail the type of AE that resulted in the discontinuation (whether serious fatal, non-serious fatal, or non-fatal).

2.3.2 Demographics and other baseline characteristics

The age of the participant at the time of OAV101 infusion will be summarized. The distribution of participants by sex, race, and ethnicity will be presented. If a participant reports multiple races, they will be categorized as “multiple races” in the summary table. Participant demographics will be summarized by weight bracket (≥ 8.5 -13 kg, > 13 -17 kg, > 17 -21 kg) and overall, for the FAS.

Demographic data will be determined using the following calculations:

If age at Screening visit 1 will be given in months or years, respectively, age in days is 30.4375 times age in months and 365.25 times age in years.

Age at Study day 1 = (Study day 1 visit date – Screening visit 1 date + age at Screening visit 1 in days)/365.25 days, expressed in years

Height/Length (in cm) = height (in inches) * 2.54

Weight (in kg) = weight (in lbs) * 0.4536

The following statistics regarding the participant’s characteristics at birth will be summarized: gestational age (weeks).

The presence of significant medical conditions obtained from medical history will be summarized. In particular, the following parameters will be summarized regarding symptoms and history of Spinal Muscular Atrophy: age at diagnosis and at symptom onset (if applicable), baseline SMA symptoms (if applicable), SMA genetic testing, family history of SMA, and number of siblings affected by SMA.

The time from SMA diagnosis to study start at Screening visit 1 is defined as the difference in days between the dates. The same approach is taken for time since first symptoms accordingly.

Age at SMA diagnosis in years is calculated as age at study start in days minus time from SMA diagnosis to study start, divided by 365.25. If diagnosis is prenatal, age at SMA diagnosis is 0 years. If diagnosis is not prenatal or unknown to be prenatal, minimum age at SMA diagnosis is 0 years.

Age at first symptoms of SMA in years is calculated as age at study start in days minus time from first symptoms of SMA to study start, divided by 365.25. Minimum age at first symptoms of SMA is 0 years.

Where appropriate, frequencies of age groups will be displayed as 0-<28 days, 28 days-<2 years, 2-<12 years, 12-<18 years, 18 years or more.

Baseline characteristics including virus SMN1 details including presence/absence of bi-allelic deletion, point mutations, and genetic modifier G>C.859, SMA type, SMN2 copy number, pre-treatment with SMA disease-modifying treatments (DMT), developmental motor milestone status, and total scores of HFMSE and RULM will be summarized by weight bracket (≥ 8.5 -13 kg, > 13-17 kg, > 17-21 kg) and overall, for the FAS. Virus serology variables include HIV, hepatitis B and hepatitis C test results. The coagulation panel includes prothrombin time (PT), International Normalized Ratio (INR) and activated partial thromboplastin time (aPTT). Duration of SMA DMT will be summarized.

Relevant medical histories and current medical conditions at baseline will be summarized by system organ class and preferred term by weight bracket and overall.

2.4 Treatments (study treatment, rescue medication, concomitant therapies, compliance)

2.4.1 Study treatment / compliance

The Safety set will be used for the analyses below. Categorical data will be summarized as frequencies and percentages. For continuous data, descriptive statistics including mean, standard deviation, median, minimum, and maximum will be presented.

The duration of administration in minutes, volume of infusion, dose administration pause during infusion, and treatment compliance (%) will be summarized by means of descriptive statistics using the safety set. Treatment compliance is defined as 100 times the dose administered divided by the planned dose, 1.1e14 vg/kg body weight.

2.4.2 Prior, concomitant and post therapies

Prior and concomitant medications and significant non-drug therapies prior to and after the start of the study treatment will be listed and summarized according to the ATC classification system.

A prior medication is defined as any medication taken prior to the date of the OAV101 infusion. A concomitant medication is defined as medication that started prior to the date of the OAV101 infusion and continued to be taken after the infusion or any medication that started on or after the date of the OAV 101 infusion. The number and percentage of participants in the safety analysis set taking prior or concomitant medications will be summarized by generic drug name

based on the WHO Drug Dictionary. Further summaries will present prior medications ongoing at Study Day 1.

2.4.3 Specific Medication Subgroups

To reduce the host immune response to the AAV-based therapy, participants will receive prophylactic prednisolone or equivalent steroid (approximately 1 mg/kg/day) 24 hours prior to the gene transfer and continuing for approximately 30 days. After 30 days of treatment, the dose of prednisolone or equivalent can be tapered for participants whose ALT values and AST values are $\leq 2 \times$ ULN.

The total number of days receiving prophylactic prednisolone or equivalent and total cumulative dose of prophylactic prednisolone administered during the study (mg/kg, derived from the prednisolone log) will be computed for each participant. Partial treatment start and end dates will be imputed as described in section 5.1.3. In case when other glucocorticosteroids were used, the doses should be converted into Prednisolone equivalent doses according to the relative potency, for example with a factor of 0.25 for hydrocortisone, 6.67 for dexamethasone and 1.25 for methylprednisolone. Dose levels at end of study will be summarized, frequencies of participants with >1 mg/kg at any time, >2 mg/kg at any time, with dose interruptions of more than 7 days and with any intravenous dosing will be reported. The number and percentage of participants with versus without prednisolone equivalent dose will also be presented per visit and weight bracket.

To compute total cumulative dose, the total dosing period is subdivided into dosing intervals represented by constant dose levels. Total doses per dose level and dosing interval are derived as the product of dose level in mg/kg and the number of days of the dosing interval. For the total cumulative dose, all products per dose level and dosing interval are summed up.

Exposure will be summarized for the Safety Analysis Set.

2.5 Analysis supporting primary objective(s)

2.5.1 Primary endpoint(s)

The primary endpoints include:

1. Incidence and severity of treatment emergent AEs and SAEs
2. Incidence of important identified and important potential risks
3. Change from baseline in vital signs, clinical laboratory, and procedure (eg ECG, echocardiogram) results

An AE is treatment-emergent, if it occurs or worsens after the start of the infusion of the investigational drug.

Important identified and important potential risks include the following AEs (see section 2.7.1.1 for detail):

- Hepatotoxicity
- Thrombocytopenia
- Cardiac adverse events
- Dorsal root ganglia toxicity

- Thrombotic microangiopathy

Vital sign parameters include height, weight, body mass index, blood pressure, respiratory rate, pulse, temperature, and oxygen saturation level. On Day 1, vital signs will be recorded pre-dose and then monitored post dose and at each visit.

Laboratory parameters in the scope of primary endpoints include platelets, troponin-I, and among chemistry variables alanine aminotransferase (ALT), aspartate aminotransferase (AST), glutamate dehydrogenase (GLDH), alkaline phosphatase (ALP), gamma glutamyl transferase (GGT), serum total bilirubin, direct bilirubin, and indirect bilirubin.

Cardiac procedures include ECG and echocardiogram. ECG parameters include QT, RR, and QTcF. Reviewed by local and central cardiologists, echocardiogram parameters include thrombus status, left ventricular ejection fraction (%), left ventricular fractional shortening (%), and left ventricular global longitudinal strain. ECG overall interpretation will be given.

2.5.2 Statistical hypothesis, model, and method of analysis

No hypothesis testing will be performed.

Incidence and severity for treatment emergent AEs and SAEs as well as important identified and important potential risks will be summarized by weight bracket and overall in the safety set. The number and proportion of participants reporting a treatment emergent AE or SAE at least once will be reported. Summaries will also be provided by MedDRA System Organ Class and Preferred Term.

Changes from baseline in vital signs and clinical laboratory results will be summarized descriptively by weight bracket and overall in the safety set. Mean, standard deviation, median, minimum, and maximum will be presented. For each applicable time point, only participants with a baseline value and a measurement for that time point will be included in the summary. Shift tables of laboratory abnormality versus baseline will be provided for minimum, maximum and final post-baseline values. For laboratory parameters of primary interest except for GLDH, direct and indirect bilirubin, additional shift tables will consider CTCAE grading, version 5. For troponin-I, any value above the upper limit of the reference range (ULN) is considered CTCAE Grade 1. Number of participants with ALT >ULN, 2xULN, 3xULN per visit will be summarized. Individual courses of and median changes from baseline in clinical laboratory results of ALT, AST, GLDH, ALP, GGT, serum total bilirubin, direct bilirubin, indirect bilirubin, platelets, and troponin-I over time will be visualized. Graphs of median changes will be per weight bracket. Graphs of individual clinical laboratory results will use normalized values as multiples of ULN.

Procedure results including ECG QTcF and overall interpretation will be summarized descriptively by weight bracket and overall.

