5.2 Exclusion criteria

Participants meeting any of the following criteria are not eligible for inclusion in this study.

1. Previous OAV101 use or previous use of any AAV9 gene therapy
2. BMI < 3rd percentile based on WHO Child Growth Standard
3. Participant with history of aspiration pneumonia or signs of aspiration (e.g., coughing or sputtering of food) within 4 weeks prior to screening
4. Anti-AAV9 antibody titer > 1:50 as determined by ligand binding immunoassay at the time of screening
5. History of gene therapy, hematopoietic transplantation, or solid organ transplantation
6. Inability to take corticosteroids
7. Concomitant use of immunosuppressive therapy, plasmapheresis, immunomodulators such as adalimumab, or immunosuppressive therapy within 3 months prior to gene replacement therapy (e.g., cyclosporine, tacrolimus, methotrexate, rituximab cyclophosphamide, IV immunoglobulin)
8. Requiring invasive ventilation, tracheostomy or awake non-invasive ventilation (standard of care nocturnal BiPAP is not considered exclusionary)
9. Administration of vaccines 2 weeks prior to infusion of OAV101
10. Awake hypoxemia (O₂ saturation <95%) or awake oxygen saturation level decrease between screening and dosing that is clinically significant, as per investigator judgment.
11. Clinically significant neurologic or neuromuscular conditions other than SMA as determined by the principal Investigator
12. Clinically significant abnormalities in laboratory test results at Screening as determined by the Investigator
13. Hepatic dysfunction (i.e. AST, ALT, bilirubin, GGT or GLDH, > ULN) at Screening (with the exception of isolated AST elevation: in the absence of other liver laboratory abnormalities, isolated AST elevation is not considered exclusionary)
14. Excluding SMA, any medically unstable condition considered clinically significant by the Investigator, including cardiomyopathy, hepatic dysfunction, kidney disorder, endocrine disorder, GI disorders, metabolic disorders, severe respiratory compromise and significant brain abnormalities at either Screening or Baseline that, in the opinion of the Investigator, would interfere with the overall interpretation of safety or efficacy of the study
15. Presence of a confirmed or suspected active infectious process from screening and up to dose administration
16. If previously treated with disease modifying therapy, participants are excluded if they received
 - less than 3 doses of nusinersen (Spinraza[®])

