2.7.3 Laboratory data

Safety laboratory data generated by the central laboratory will be used in all analyses. Safety laboratory data generated by local lab will only be listed. In data listings, per parameter, values will also be given as multiples of upper normal range limits.

Laboratory parameters include hematology, chemistry and urinalysis variables.

Changes in selected safety laboratory variables are primary endpoints. For details, see Section 2.5.

Hematology variables include: hematocrit, hemoglobin, red blood cell (RBC) count, white blood cell (WBC) count, differential blood count (in measured values and % of WBC; neutrophils, lymphocytes, monocytes, eosinophils, basophils, bands), mean corpuscular volume

(MCV), mean corpuscular hemoglobin (MCH), mean cell hemoglobin concentration (MCHC), and platelets.

Chemistry variables include: ALT, ALP, AST, blood urea nitrogen (BUN), calcium, creatinine, gamma glutamyl transferase, glucose, serum total bilirubin, direct bilirubin, indirect bilirubin, total creatine kinase (CK), chloride, phosphorus, sodium, potassium, lactate dehydrogenase (LDH), GLDH, troponin-I, and bicarbonate.

Urinalysis variables include: specific gravity, pH, ketones, glucose, protein, blood, leukocyte esterase, nitrites, bilirubin, RBC count, WBC count, yeast, squamous epithelial cells, casts, crystals, bacteria.

Clinical laboratory test results will be summarized at each visit including End of Study/Early Termination, for minimum, maximum and final post-baseline values. Urinalysis variables will only be listed.

Laboratory data values will be categorized as low, normal, or high, based on normal ranges of the laboratory used in this study. Shift tables from baseline to minimum value, maximum value, and final values will be created. The shift tables will cross tabulate the frequency of participants with baseline values below/within/above the normal range versus minimum/maximum/final values below/within/above the normal range.

The number and percentage of participants meeting the criteria for ALT and bilirubin defined in Table 16-1 of the protocol will be summarized by weight bracket and overall including potential Hy's Law cases. Potential Hy's Law cases will be presented for maximum post-baseline values as combined, even if criteria are fulfilled at different times during the follow-up.

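### As written, the CTCAE shift table for troponin-I can show only Grade 0 or Grade 1, so it cannot separate small from large elevations or show worsening from an elevated baseline

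*SAP*

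**What the plan says.** SAP 2.5.1 lists troponin-I among the laboratory parameters that belong to the primary endpoints: "Laboratory parameters in the scope of primary endpoints include platelets, troponin-I", followed by the liver chemistry variables.

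SAP 2.5.2 then sets out two kinds of shift table. The first compares abnormality status at baseline with the minimum, maximum and final post-baseline values. SAP 2.7.3 defines its categories: "Laboratory data values will be categorized as low, normal, or high, based on normal ranges of the laboratory used in this study". The second kind is extra: "For laboratory parameters of primary interest except for GLDH, direct and indirect bilirubin, additional shift tables will consider CTCAE grading, version 5". Troponin-I is not among the exceptions, so it gets this table. The next sentence fixes its grading: for troponin-I, "any value above the upper limit of the reference range (ULN) is considered CTCAE Grade 1".

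Neither document gives a troponin-I criterion for Grade 2 or above. SAP 2.5.2 also plans counts of participants above one, two and three times ULN at each visit, but for ALT only.

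**The concern.** A grade-shift table is meant to cross-tabulate baseline grade against worst grade, so that a reader can see how many children got worse and by how much. If every value above ULN has the same grade, the table cannot do that. The label Grade 1 also carries a meaning of severity, which here is assigned before any data are seen. A reader who finds troponin-I beside parameters that are truly graded could take the lack of higher grades as a result, when it would follow from the rule whatever the data.

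This matters somewhat more for troponin-I than for a routine analyte. Safety is the primary objective. Cardiac adverse events are an AESI category (Protocol 10.1.1). Protocol 1.1 names the heart as a target organ of toxicity in mice and monkeys. Protocol 6.2 names troponin I elevation as a possible result of the immune response to the capsid.

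**Working it through.** The plan states no figure on this point, so there is none to reproduce. The check is to apply the rule as written.

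**Inputs**
- Grading rule (SAP 2.5.2): with x = troponin-I divided by ULN, grade = 1 if x > 1, otherwise 0.
- Normal-range category (SAP 2.7.3): high if x > 1, normal otherwise. The low category plays no part in elevations.
- Values of x: assumed, because the documents contain no troponin data. Baselines tried were 0.5, 1.0, 1.2, 2 and 5. Post-baseline values tried were 0.5, 1.0, 1.2, 2, 5, 10, 50 and 200.

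**Results** (two of the baselines shown)

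| Baseline (x ULN) | Post-baseline (x ULN) | CTCAE shift | Normal-range shift | Change (x ULN) |
|---|---|---|---|---|
| 0.5 | 1.2 | 0 to 1 | normal to high | 1.2 - 0.5 = 0.7 |
| 0.5 | 200 | 0 to 1 | normal to high | 200 - 0.5 = 199.5 |
| 1.2 | 2 | 1 to 1 | high to high | 2 - 1.2 = 0.8 |
| 1.2 | 10 | 1 to 1 | high to high | 10 - 1.2 = 8.8 |
| 1.2 | 200 | 1 to 1 | high to high | 200 - 1.2 = 198.8 |

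- Over the whole grid only four cells occur: 0 to 0, 0 to 1, 1 to 0 and 1 to 1.
- From the baselines above ULN (1.2, 2 and 5), the number of upward shifts is 0 for every post-baseline value from 1.2 to 200.
- Grade 2 or higher cannot occur. This follows from the rule and does not depend on the multiples chosen.
- For elevations, the two shift tables divide the values at the same point (x > 1). The CTCAE table therefore adds a severity label to the normal-range table but no information.

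**Can a child start above ULN?** Exclusion 13 in Protocol 5.2 sets an explicit ULN limit for liver tests. Troponin-I has no such limit and falls under the general criterion, "Clinically significant abnormalities in laboratory test results at Screening as determined by the Investigator". Entry above ULN is therefore possible. The documents do not say how often it would happen.

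**Where does the size of an elevation still appear?**
- Change-from-baseline summaries by weight bracket and overall, with the maximum among the statistics (SAP 2.5.2).
- Summaries of minimum, maximum and final post-baseline values (SAP 2.7.3).
- Plots of median change by weight bracket, and individual courses: "Graphs of individual clinical laboratory results will use normalized values as multiples of ULN" (SAP 2.5.2, troponin-I named among the plotted parameters).
- Listings that also give each value as a multiple of ULN (SAP 2.7.3).

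**The case against.** The strongest reply is that little is lost. The primary endpoint is change from baseline, and the CTCAE tables are an add-on that feeds no hypothesis, decision or stopping rule. With about 24 to 30 children, individual plots and listings can be read one by one, and a child who rose from 1.2 to 20 times ULN would stand out there. Cardiac severity is not judged from this table either. Cardiac AESIs are found through MedDRA queries and summarised as severe, serious and drug-related (SAP 2.7.1.1.1). ECG and echocardiogram results are primary parameters in their own right. All of this stands. A reader might infer from the grading rule that the SAP hides worsening of troponin-I. The documents do not support that, because several other planned outputs show it.

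A second reply is that the sentence may set only the entry threshold for Grade 1 and leave higher grades to CTCAE version 5, which the preceding sentence invokes. That is possible, so it would be too strong to say that the sponsor intends a table with no higher grade. But the sentence covers any value above ULN and names no higher grade, so a programmer who follows it would code every elevation as Grade 1. Whether CTCAE itself offers a higher grade for troponin cannot be settled from these documents and is not assumed here.

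A third reply concerns the remedy. A full cross-tabulation of baseline by maximum in, say, five ULN bands has 5 x 5 = 25 cells for the 6 to 10 children planned per bracket, and would be mostly empty. This also stands, and the fix below avoids it.

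None of these replies makes the table informative. Plots and listings do not tabulate, by weight bracket, how many children reached a given level from a given baseline status.

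**Conclusion.** The point holds within limits. Under the literal reading of SAP 2.5.2, the troponin-I CTCAE shift table separates only values above ULN from all others. It cannot distinguish small from large elevations, it cannot show worsening in a child already above ULN at baseline, and the low/normal/high table does not fill the gap.

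The conclusion rests on taking the sentence as written and on the lack of any higher-grade criterion elsewhere in the documents. The number of children affected is unknown, since neither expected troponin values nor the share above ULN at baseline is given. The consequence is confined to the tabulated grading, so this is a minor point that is worth correcting because the correction is cheap.

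**What to change.** 1. State in SAP 2.5.2 whether higher CTCAE version 5 grades apply to troponin-I. If they do, reword the sentence as the threshold for Grade 1 and give the criteria for the higher grades.
2. If they do not, drop the Grade 1 label for troponin-I. Add counts of participants whose maximum post-baseline value exceeds pre-specified multiples of ULN, by weight bracket and overall, split by baseline status (not above ULN, above ULN). This follows the counts already planned for ALT. With three thresholds, as for ALT, each bracket needs 2 x 3 = 6 counts.

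The cost is SAP wording and a little programming. Values as multiples of ULN are already derived for the plots and listings, and no new data, visits or participants are needed. The downside is that the cut-points are descriptive and must be fixed before database lock. A child whose baseline already exceeds the highest cut-point would still have to be followed in the change-from-baseline summary and the individual plot.
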